Feasibility of recruitment: In 2019, 987 patients with OUD and CP diagnoses of back pain, arthritis, or neuropathy were hospitalized at Montefiore. Co-morbidities that would be exclusions for this RCT were: BUP treatment (7%), methadone treatment (31%), severe alcohol use disorder (8%), and severe benzodiazepine use disorder (2%). Removing patients with ≥ 1 exclusion leaves 640 potential participants. In a prior RCT of BUP treatment for hospitalized patients, 21% of eligible patients were enrolled.¹⁸ Using a more conservative estimate of enrolling 14% of eligible patients, enrolling 270 participants in 3 years will be feasible (640 eligible/year x 14% enrollment rate x 3 years = 270 participants).

D.2.5 Screening and Randomization: Initial screening and consent: Participants will be screened for eligibility and exclusion criteria by a trained research coordinator using a brief questionnaire. Participants will be informed of study procedures, risks and benefits of study participation, tested for their understanding, and they will provide written consent. During enrollment, female participants will have urine pregnancy tests.

Randomization will be unblinded, stratified, and blocked, with a 1:1 ratio across the two arms. To ensure balanced distribution between arms, we will stratify by OUD severity (misuse/mild vs. moderate/severe), heroin use (past 30 days, yes vs. no), and mood disorders (yes vs. no). We will randomize in blocks of 4-8 to ensure comparison groups of equal size. To ensure concealment of allocation, a centrally-located data manager will generate allocation sequences (with SAS Proc Plan) and store sequences in a password-protected file.

D.2.6 Participant tracking: We will use procedures that we have developed to retain people who use drugs in previous research, in which we have had an 84% retention rate over 6-month-follow-up.¹¹⁰ Participants will complete locator forms at enrollment and update them at all research visits. Information will include: 1) participants' addresses, phone numbers, and social security numbers; 2) contact information of family or friends; 3) contact information of participants' community-based organizations and case managers; and 4) participants' "hang out" locations.

Table E-2. Microdosing Initiation Dosing Schedule

Day	Microdosing			Standard Induction		
	Full agonist	BUP	Daily Total	Full agonist	BUP	Daily Total
1	Full dose	0.5 mg q12	1 mg	STOP	--	--
2	Full dose	1 mg q8	3 mg	--	2 mg q4 h	8 mg

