Secondary OUD outcomes include illicit opioid use and BUP retention. **Illicit opioid use** will be examined as the number of days of illicit opioid use (defined as self-reported use of heroin, fentanyl, or non-prescribed opioid analgesics) in the prior 30 days based on the Addiction Severity Index (continuous).¹¹⁹ Because urine drug testing (UDT) only captures opioid use in the prior 24-72 hours, it is a less sensitive measure of substance use over time; however, UDT results will be a secondary outcome measure. **BUP retention** will be

Table E-4. Ecological Momentary Assessment (EMA) Measures

Construct	Measure
EMA opioid- and pain-related symptoms	
Opioid withdrawal	Subjective Opioid Withdrawal Scale (SOWS)
Opioid craving	Visual analog scale
Pain intensity	Adapted BPI pain severity subscale
Anxiety	Generalized Anxiety Disorder-7 (GAD-7)
Exploratory EMA outcomes	
Illicit opioid use	Self-report
BUP dose	Self-report
Pain treatment	Self-report

*All measures will occur at bursts 1 & 2 weeks, and 1, 2, & 3 months

defined as having a BUP prescription written the following number of days after baseline: 30-60 days (1-month retention); 90-120 days (3-month retention); and 180-210 days (6-month retention). To be retained at 3 and 6-months, participants will be required to have been retained at previous time points.⁴⁶ All OUD outcomes are consistent with elements of the Opioid Use Disorder Cascade of Care.¹²⁰

Secondary pain outcomes include pain intensity, pain interference, and quality of life. *Pain intensity* will be measured using the Brief Pain Inventory (BPI).¹²¹ We will use the mean of 4 items that assess pain intensity over the past 24 hours on a scale of 1-10 (1=minimal pain, 10=intense pain). We will use the mean of these 4 items. *Pain interference* will be measured using the pain interference scale from the BPI, which is a 7-item instrument measuring the impact of pain on daily activities and physical functioning. It is rated on a scale of 1-10 (1=minimal interference, 10=high interference). We will use the mean of these 7 items. *Quality of life* will be measured using the PROMIS-Preference Scoring System (PROP-Pr), which is described in detail as part of the cost-effectiveness analyses below (see D.4.1).¹²²⁻¹²⁴ In our main analyses, we will examine changes from baseline to 3 months for all pain outcomes; in additional analyses, we will examine sustainability at 6 months.

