Other covariates: We will include covariates that may be associated with study outcomes including: sociodemographic characteristics (age, race/ethnicity, sex, employment, housing, insurance), opioid withdrawal and craving,^{111,125} adjunctive withdrawal medications (e.g., clonidine, loperamide), pain treatments including medications (e.g., NSAIDs, gabapentin) and other forms of treatment (e.g., physical therapy, steroid injections, surgery), mood symptoms (anxiety and depression),¹²⁶⁻¹²⁸ and prior OUD treatment. We will also include holistic outcome measures developed by the IMPOWR Coordination and Dissemination Center with people with lived experience (RFA-DA-21-029) and collaborate with the IMPOWR-ME Stakeholder Board to ensure we include other measures important to them.

D.2.11 Analytic plan Aims 1 and 2: Main analyses will be completed using an intention-to-treat approach.

[figure not shown]
Preliminary analyses. We will first review and summarize data using descriptive summaries and graphical analyses to ensure that values are within appropriate ranges, to check for outliers and abnormal values, and to verify that the distributions of measures meet the assumptions of the statistical tests that are planned as described below. We will also explore whether the microdosing and TAU groups are equivalent on potential confounding variables (age, sex, race/ethnicity, baseline substance use, and mood symptoms).

Missing data. For missing data, we will use multivariate multiple imputation using the fully conditional specification method.¹²⁹ We will repeat imputations five times, and then we will compare statistical results using datasets that include imputed values and the dataset that drops missing values. This will guide interpretation of our assessment of the impact of missing data, as well as, our interpretation of overall results.

Aim 1: To test the effectiveness of microdosing (vs. TAU) on OUD outcomes.

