effect of opioid- and pain-related symptoms (e.g., withdrawal). The mediational effect is calculated as the product of the effect from intervention to the mediator, and the effect from the mediator to the outcome. To account for the influence of the baseline measures (e.g., sociodemographic characteristics) on the outcome and the mediator, we will use a partial correlation matrix as the input matrix. This will be created by statistically parsing out the effects of the baseline measures cited above on the mediator and the outcome variable. Our proposed model will be estimated using Mplus.¹³⁰ Overall model fit will be assessed by: (1) the root mean

square error of approximation (RMSEA), (2) Bentler's comparative fit index (CFI),¹³¹ and (3) the standardized root mean square residual (SRMR). To account for non-normal distribution of the model variables (e.g., BUP uptake), we will use Mplus's maximum likelihood with robust standard errors (MLR) as the estimator.

Aim 2: To test the effectiveness of microdosing (vs. TAU) on pain outcomes.

H₃: The microdosing arm (vs. TAU) will have less pain intensity and interference, and improved quality of life. We will use separate mixed effects linear regression models to compare each pain outcome from baseline to 3 months. Main analyses will use data from in-person visits at baseline, 1 week, 1 and 3 months. Study arm will be considered a fixed effect, and participant and time will be considered random effects. In additional analyses, we will include key variables mentioned above as covariates and potential confounders if they differ by study arm. We will also examine sustainability of outcomes at 6 months.

H₄: Improvements in H₃ will be mediated by OUD outcomes. Based on the model described in **Figure E-4**

and similar to the analyses for H2 (see above), we will use structural equation modeling to determine whether improvements in pain outcomes are due to improvements in OUD outcomes. For example, when the dependent variable is pain intensity, we will calculate the standardized total effect from the intervention (BUP microdosing) to pain reduction at 3 months, as well as the standardized mediational (i.e., indirect) effect of BUP uptake, BUP retention, and illicit opioid use. For these analyses, our primary mediator is BUP retention. We will use both the EMA data (5 random reports per day) and data from in-person visits at baseline, 1 week, 1 and 3 months.

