microdosing (nearly 100%), we will use a more conservative estimate of treatment uptake from our experience with microdosing (61%). In a controlled trial of standard induction to transition patients with CP from full opioid agonists to BUP, only 24% were successful with BUP uptake.⁵⁸ To detect a difference of this size in BUP uptake, we would only need 27 participants in each arm to assure 80% power. However, we will recruit a larger sample to account for the possibility that uptake will be greater than 24% in the TAU arm (see **Table E-5**). Even with study attrition, we will be

able to assess BUP uptake for all participants based on medical record extraction,

For pain outcomes, we based our power calculations on expected changes in pain intensity from baseline to 3 months. Our pilot data (see D.1.1) suggests that mean (SD) pain intensity score will be 7.3 (± 1.6) at baseline for all participants. With a sample of 270 participants (135 per arm), the minimum effect size (Cohen's d) that can be detected with power of 80% is 0.34. This effect size corresponds to a difference between arms (microdosing vs. TAU) of 8.4% for participants'

reduction in pain scores (assuming that the SD of change is 1.8). Note that the SD for the pain score change is greater than that of the pain intensity score at each time point due to the intra-participant correlation in pain intensity over time. Because pain reduction is only considered for participants with BUP uptake, attrition is already incorporated into these estimates.

D.3 Aim 3a) Examine factors influencing reach, adoption, implementation, and maintenance of the microdosing protocol.

D.3.1 Overview and hypotheses. In this hybrid type 1 effectiveness-implementation trial, we will use RE-AIM and CFIR frameworks to guide Aim 3a, in which we will use qualitative and quantitative methods to describe multi-level factors influencing reach, adoption, implementation, and maintenance of BUP microdosing.

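### The pain power statement claims to allow for attrition, but its figures assume 3-month scores from all 135 per arm, and the reason given conflicts with the intention-to-treat pain analysis

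*Combined protocol and SAP*

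**What the plan says.** D.2.12 bases the pain calculation on the change in pain intensity from baseline to 3 months: "With a sample of 270 participants (135 per arm), the minimum effect size (Cohen's d) that can be detected with power of 80% is 0.34". It converts this to an 8.4% difference between arms, using a baseline mean of 7.3 and an SD of change of 1.8. It then adds: "Because pain reduction is only considered for participants with BUP uptake, attrition is already incorporated into these estimates". The section gives no attrition rate and no reduced sample size. For the primary outcome it deals with attrition separately, because the team will be "able to assess BUP uptake for all participants based on medical record extraction".

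The analysis sections read differently:

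- D.2.11, opening: "Main analyses will be completed using an intention-to-treat approach".
- D.2.11, H3: "We will use separate mixed effects linear regression models to compare each pain outcome from baseline to 3 months". Study arm is the fixed effect and no uptake condition appears.
- D.2.11, Missing data: "For missing data, we will use multivariate multiple imputation using the fully conditional specification method".
- E.2.10: "In our main analyses, we will examine changes from baseline to 3 months for all pain outcomes".

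The only retention figure is in D.2.6, from the team's earlier research: "we have had an 84% retention rate over 6-month-follow-up".

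**The concern.** Two things look wrong. First, a detectable effect quoted for 135 per arm cannot also include attrition unless a smaller number was used in the calculation, and none is shown. Pain scores come from questionnaires at study visits (D.2.8, D.2.9), so participants who miss the 3-month assessment have no score. The Aim 2 figure would then be more favourable than the expected data support.

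Second, the reason offered is that pain reduction is looked at only in those who take up BUP. Uptake is the primary outcome. It is measured after randomisation and is expected to differ by arm (61% v 24%). A pain comparison restricted in that way would set about 82 microdosing participants against about 32 TAU participants, selected by different processes, and would lose the protection of randomisation. The sentence therefore also puts in doubt who is in the Aim 2 comparison.

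**Working it through.** **Inputs.** From D.2.12: 135 per arm, 80% power, SD of change 1.8, baseline mean 7.3 (SD 1.6), uptake 61% and 24%. From D.2.6: 84% retention at 6 months. Assumed: two-sided alpha 0.05, since none is stated; follow-up of 84%, 90% or 95% at 3 months, since no 3-month rate is given.

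**Formulas.** Two-sample comparison of mean change, normal approximation:

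- d = (1.960 + 0.8416) × √(2/n) = 2.8016 × √(2/n)
- points = 1.8 × d; percent = points / 7.3
- power at the stated effect = Φ(0.341/√(2/n) − 1.960)

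**Step 1: the plan's figure.** With n = 135: d = 2.8016 × √(2/135) = 0.341; 1.8 × 0.341 = 0.614 points; 0.614/7.3 = 8.41%. Both stated values are reproduced with no loss. One-sided 0.05 at 135 per arm gives 0.303, which does not match.

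**Step 2: with incomplete follow-up (complete cases).**

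| 3-month follow-up | n per arm | d | Points | Percent | Power at d 0.341 |
|---|---|---|---|---|---|
| 100% | 135 | 0.341 | 0.614 | 8.41% | 80% |
| 95% | 128.25 | 0.350 | 0.630 | 8.63% | 78.0% |
| 90% | 121.5 | 0.359 | 0.647 | 8.86% | 75.7% |
| 84% | 113.4 | 0.372 | 0.670 | 9.17% | 72.8% |

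The detectable difference grows by 1/√(follow-up): 2.6%, 5.4% and 9.1%, whatever the SD.

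**Step 3: with an uptake restriction.** 135 × 0.61 = 82.35 and 135 × 0.24 = 32.4. With 82 v 32, d = 2.8016 × √(1/82 + 1/32) = 0.584, or 1.05 points (14.4%). This is far from 0.34, so no uptake restriction is in the stated figure.

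**Step 4: sensitivity to baseline adjustment.** Assume SD 1.6 at both times. The correlation implied by an SD of change of 1.8 is 1 − 1.8²/(2 × 1.6²) = 0.367, and the residual SD is 1.6 × √(1 − 0.367²) = 1.488. The detectable difference is then 0.507 points at n = 135, 0.535 at 121.5 and 0.554 at 113.4. The level is lower; the proportional loss is the same.

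**Step 5: the sentence read as an assumption about where benefit arises.** If benefit came only through uptake, an arm difference of 0.614 would need 0.614/(0.61 − 0.24) = 1.66 points more reduction per participant with uptake than per participant without. For orientation only, the pilot fall in D.1.1 was 7.3 − 6.0 = 1.3 points, at 6 months and uncontrolled.

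**The case against.** The strongest reply is that the losses above belong to an analysis the plan does not use. H3 is a mixed model with baseline, 1-week, 1-month and 3-month scores, missing data are multiply imputed, and questionnaires can be completed virtually. Under the baseline-adjusted assumptions of step 4, the detectable difference at 84% follow-up is 0.55 points, still below the plan's 0.61. Power at 0.614 would be Φ(0.614/(1.488 × √(2/113.4)) − 1.960), about 87%. This part stands: whether 0.61 is optimistic for the final model is not settled. But the main H3 model names no baseline covariate, the 3-month SD is assumed, and a margin from another model does not mean that the quoted figure allows for attrition.

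A second reply is that the analysis plan governs, and that the sentence only expresses the expectation that pain relief comes from BUP, as D.5 says. That reading is plausible and fits intention-to-treat. Even so, no dilution step is shown, and non-uptake is not the same as a missing score. The step 5 comparison is weak evidence: it treats a detectable difference as an expected one, fixes TAU uptake at 24% although D.2.12 allows for more, and sets it beside an uncontrolled 6-month change. It is an illustration and carries no weight in the conclusion.

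A third reply is that alpha is unstated, and one-sided 0.05 with about 107 per arm would also give 0.34. The plan, however, ties 0.34 to 135 per arm.

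**Conclusion.** The concern holds. The arithmetic behind d = 0.34 and 8.4% is correct for 135 observed scores per arm; the statement that attrition is covered is not. Read plainly, the reason given for it contradicts D.2.11, and read generously it still makes no allowance for missing 3-month scores. The size is modest. Like for like with the plan's own method, the detectable difference rises by 0.03 points at 90% follow-up (0.61 to 0.65 after rounding) and by 0.06 points at 84% (0.61 to 0.67), with power at the stated effect of about 76% and 73%. These figures rest on two-sided alpha 0.05, complete cases and assumed follow-up rates; the 84% is a 6-month rate from other work. Pain is a secondary outcome, and neither the primary analysis nor the sample size changes. It should be fixed because the plan describes its figure wrongly and leaves two readings of the pain population.

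**What to change.** Delete the last sentence of the pain paragraph in D.2.12 and put in its place:

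> Pain outcomes will be analysed in all randomised participants as assigned, whether or not they take up BUP. We expect [x]% to provide a 3-month pain score; as a complete-case approximation, the detectable difference at that rate is [y].

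Worked values for y: d 0.36 (0.65 points, 8.9%) at 90%, or d 0.37 (0.67 points, 9.2%) at 84%. State alpha and sidedness alongside. If the team prefers a figure for the planned model, it should give the covariates, SD and correlation used. If the sentence was meant as an assumption about where benefit arises, say so and show the between-arm difference it implies.

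With D.2.11 as it stands, this is a wording change: no added patients, no effect on the primary analysis, and a slightly less favourable secondary figure on the complete-case basis. If an uptake-only comparison was really intended, confirming all randomised participants is a change of analysis population and should be recorded as such.

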B.3 Fear of withdrawal prevents people from initiating BUP. Needing to transition to BUP from opioid agonists (i.e. heroin or prescription opioids) prevents people with opioid misuse or OUD from starting BUP. There are two challenges: 1) patients must typically avoid opioids for 24-72 hours before starting BUP; and 2) *precipitated or persistent withdrawal* during BUP induction can lead to early treatment cessation. If BUP is taken too soon after full opioid agonists, opioid-dependent people will experience precipitated withdrawal when BUP displaces other opioids at mu opioid receptors while providing only partial agonism. Relative reduction in opioid agonist activity is experienced as withdrawal,^{44,50,51} which can reduce interest in BUP treatment.^{52,53} People taking prescribed opioids express fear of stopping opioids due to worsening pain and withdrawal.^{9,10,54-57} Two early studies that attempted to transition patients with CP and likely OUD from prescription opioids to BUP highlight induction challenges. In one trial, 21 patients consented to transition from prescription opioids to BUP, but only 12 took BUP and 4 successfully completed induction.⁵⁸ In a retrospective pain clinic study, only 104 of 271 patients receiving prescription opioids who were offered BUP successfully transitioned to BUP.⁸ One study of 76 CP patients with opioid misuse used an inpatient protocol to transition to BUP; the protocol included conversion to intravenous opioids and giving small doses of intramuscular or sublingual BUP.⁵⁹ This worked, but elective hospitalization for BUP induction is too resource intensive to be generalizable. Even when BUP induction is successful, as many as 28% of patients drop-out during the first week of treatment, likely due to

Figure E-1. Study summary

uncontrolled craving and withdrawal.⁶⁰⁻⁶⁴ Improved BUP induction protocols are needed.

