3	Full dose	2 mg q8	6 mg	--	8 mg BID	16 mg
4	Full dose	4 mg q8	12 mg	--	8 mg BID	16 mg

D.2.7 Clinical Protocols: Microdosing**(Experimental arm):**

Participants randomized to microdosing will start low-dose BUP while continuing a full opioid agonist according to a 4-day protocol (see **Figure E-2 & Table E-2**). Participants will be assessed for opioid withdrawal using the clinical opioid withdrawal scale (COWS) before the first BUP dose and 30 minutes after each administered dose while hospitalized.¹¹¹ A full opioid agonist will be continued until day 5 of the protocol.^{112,113} If patients are planned for discharge before completing

microdosing, they will receive at the time of discharge pre-packed medication clearly marked with the timing for each dose, instructions on how to take the medication and when to stop full agonist opioids. Opioid withdrawal will be assessed with the Subjective Opioid Withdrawal Scale (SOWS) via telephone.

Rationale for 5-day protocol: Published microdosing protocols range from 3 to 7 days or more. From 2012-2016, the mean length of stay for patients at Montefiore Medical Center with an opioid positive urine drug test was 7.62 days (95% CI: 7.44-7.80). Some evidence suggests that rapid titration to maintenance BUP treatment dosages prevents drop-out,¹¹⁴ but rapid titration could increase precipitated withdrawal risk, therefore, we developed our protocol in the middle of the published range.

TAU (Control arm): Participants randomized to TAU will receive a standard BUP induction following clinical guidelines. Full opioid agonists will be stopped and a clinician will assess for withdrawal using the COWS scale. If participants have a COWS score of ≥ 8 they will be eligible to receive a 2 mg BUP dose. Participants will be reassessed for withdrawal 30 minutes after receiving their first BUP dose.

Withdrawal management: Participants with COWS score increases of $\geq 50\%$ or an absolute increase of 4 or more will be considered to have precipitated withdrawal. If this occurs, induction will be postponed to the following day. Clinicians can administer non-opioid adjunctive medications (i.e., clonidine, loperamide) during induction based on hospital protocols. Medication use will be considered a covariate in analyses with withdrawal symptoms as an outcome.

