D.3.2 RE-AIM and CFIR frameworks. The RE-AIM framework allows us to quantify implementation processes of Reach, Effectiveness, Adoption, Implementation, and Maintenance. We will determine how completely hospitals can deliver microdosing and whether protocols are continued at study sites 3 months after completing the RCT. Because RE-AIM may be less well-suited to explore how broader factors influence implementation, we will also apply the CFIR framework, which is comprehensive, widely used in substance use research, and explains how environmental context shapes implementation.^{132,133} CFIR's 5 domains include: interventions, outer setting, inner setting, individuals involved, and process. RE-AIM will be used to construct quantifiable measures; complementary qualitative methods guided by CFIR will be applied to understand the factors that influence these measures. Both frameworks will allow us to better disseminate the BUP microdosing protocol, which will allow for greater transparency, reproducibility, and scientific contribution.

D.3.3 Quantitative methods. Using RE-AIM, we will first define reach, adoption, implementation, and maintenance measures (**Table E-6**) derived from program logs and EHR data. The primary implementation measure will be the % of participants in each arm who *complete induction* (defined as receiving ≥ 1 BUP dose on induction day). Quantitative implementation benchmarks: We anticipate that 14% of screened patients with CP and OUD will enroll in the RCT,¹⁸ that $> 95\%$ of enrolled participants will be assessed for BUP induction, and that $> 70\%$ of participants who initiate BUP will be linked to outpatient BUP treatment.¹⁸ If we are unable to meet these benchmarks annually, then we will retrain study coordinators and clinical staff in recruitment, pharmacy, and referral procedures.

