D.3.4 Qualitative data collection: [name] (early-stage investigator) or an RA will conduct 45-60 minute semi-structured interviews with participants and hospital providers. We will sample 20-30 participants in the microdosing arm, including those who do and do not initiate BUP. Participant interviews will occur after BUP induction. We will also interview 10 hospital providers who care for study participants. After completing interviews, if new themes continue to emerge, we will randomly select additional participants until thematic saturation is achieved. Patient interviews: We will develop a semi-structured interview guide with input from people with lived experience that asks open-ended questions about patients' experiences with induction, particularly acceptability and reasons for BUP initiation or lack of initiation, and whether BUP helps with pain. Provider interviews will elicit information about factors associated with achieving RE-AIM outcomes (reach, effectiveness, adoption, implementation, and maintenance). The interview guide will be informed by CFIR domains regarding implementation of induction and referral procedures at the hospitals. Using the 5 CFIR domains, we will probe how various factors enable or hinder implementing the microdosing protocol. This includes ease of initiating BUP (e.g., feasibility), inner organization (e.g., fit and acceptability within hospitals), outer setting (e.g., social factors influencing clinical practice), perceptions of individuals involved (e.g., BUP

Table E-6: Aim 3a Implementation Measures

Construct	Quantitative Measures	Qualitative Assessment
Reach	# and % of pts with CP and OUD screened # and % of pts with CP and OUD enrolled # and % of pts with CP and OUD ineligible Rates of enrollment at each hospital	Log of verbatim reasons patients stated for declining enrollment
Adoption	# and % of participants assessed for induction # and % of participant completing induction # and % of participants referred for outpatient BUP treatment # and % of participants linked to outpatient BUP treatment	Interviews with participants about their experience, including barriers and facilitators to treatment initiation and linkage
Implementation	# and % of participants who receive ≥ 1 dose of BUP within assigned induction protocol Intervention fidelity check-list	Interviews with providers about barriers and facilitators to implementation

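### The primary implementation measure in D.3.3 labels a single buprenorphine dose on an undefined induction day as completed induction, so it reports initiation and cannot show completeness of delivery

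*Combined protocol and SAP*

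**What the plan says.** D.3.3 sets the measure: "The primary implementation measure will be the % of participants in each arm who" complete induction, "defined as receiving ≥ 1 BUP dose on induction day". It gives no minimum dose, no required number of doses and no definition of induction day. D.3.2 says that the study will establish how fully hospitals deliver microdosing.

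Table E-6 has two related rows. Under Adoption it counts the number "and % of participant completing induction". Under Implementation it counts the number "and % of participants who receive ≥ 1 dose of BUP within assigned induction protocol".

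On the inductions themselves, D.2.7 says: "Participants randomized to microdosing will start low-dose BUP while continuing a full opioid agonist according to a 4-day protocol". COWS is measured before the first microdose, but no threshold is stated. In the treatment-as-usual (TAU) arm, full agonists are stopped first, and the first 2 mg dose requires a COWS score of at least 8. D.2.7 also provides for microdosing participants who leave hospital with part of the schedule still to take. In its withdrawal paragraph it postpones induction to the next day if withdrawal is precipitated.

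In B.3, the protocol describes an earlier trial in which 21 patients consented but "only 12 took BUP and 4 successfully completed induction".

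**The concern.** Elsewhere the protocol uses completion to mean reaching the end of the induction schedule. In D.3.3 it means taking one dose. A hospital reading a high completion percentage would conclude that the multi-day protocol can be delivered, when the figure shows only that dosing began. This is the one implementation measure that the plan names as primary.

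A second difficulty is that the measure is reported by arm. The first dose opens the microdosing schedule, whereas in TAU it follows agonist cessation and a withdrawal threshold. Set side by side under the label of completion, the two percentages invite a comparison that they do not support.

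**Working it through.** The plan gives no expected rate, sample size or power for this measure, so there is no figure of its own to reproduce. The 27 per arm in D.2.12 concerns BUP uptake at day 7 and is not affected.

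**1. What one dose represents.** Table E-2 schedules microdosing at q12 on Day 1 and q8 on Days 2 to 4.
- Doses: 2 + 3 + 3 + 3 = 11.
- Total: 1 + 3 + 6 + 12 = 22 mg.
- The first dose is 1 of 11, and 0.5/22 = 2.3% of the four-day total.
- In TAU, the first dose is 2/8 = 25% of the Day 2 total.

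**2. What induction day could mean.**
- Protocol Day 1: microdosing has doses scheduled. Table E-2 schedules no BUP for TAU that day, so TAU would score 0% by design.
- The day of the first scheduled BUP dose: one dose suffices in both arms, but only TAU must first meet a withdrawal condition. A TAU participant who reached the threshold a day late would not count.
- Any day within the assigned protocol: the measure then coincides with the Implementation row of Table E-6.

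Under the first two readings a single 0.5 mg dose on Day 1 counts as completion, and under the third a single dose on any day does. It would fail to count only if induction day meant a late day of the schedule, and no text says so.

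**3. Conflict with the protocol's own usage.**
- D.2.7 treats a participant discharged part-way through the schedule as not yet finished. D.3.3 counts that participant as complete from the first dose.
- D.2.7 postpones induction when a dose precipitates withdrawal. D.3.3 scores that participant as complete on the strength of the same dose.
- B.3 separates the two steps: 12/21 = 57% took BUP and 4/21 = 19% completed. Of those who took BUP, 8/12 = 67% did not complete. A one-dose measure sees none of that loss.

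**4. Room for the two to diverge here.** Table E-1 requires a planned stay of only 48 hours. Over Days 1 and 2 the microdosing schedule holds 2 + 3 = 5 doses, which leaves 6 of 11 that may fall after discharge.

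**5. Can an arm advantage be sized?** B.3 and D.1.4 give the only figures.
- One-dose rule: at most 18/18 = 100% for microdosing, assuming that everyone who attempted it took a dose, against 12/21 = 57%. The gap is 43 points.
- Success or completion: 11/18 = 61% against 4/21 = 19%. The gap is 42 points, or 37 if the 24% that D.2.12 attributes to the same study is used (61 − 24).

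The loose rule raises both arms. If one assumes 95 to 100% first dosing in microdosing and 57% (B.3) to 94% (B.6) in TAU, the one-dose gap runs from 95 − 94 = 1 point to 100 − 57 = 43 points. The documents do not narrow that range.

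**The case against.** The strongest reply is that this is a descriptive measure under Aim 3a. D.3.3 reports a percentage by arm with no test, hypothesis or success threshold. The rule is worded identically for both arms, and an easier first dose is the mechanism that microdosing is meant to exploit. All of that stands.

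A reader might infer that the measure is biased in favour of microdosing by construction. The documents do not support this. The stages differ, but a higher first-dose rate in microdosing would be partly a real effect. The protocol's own figures give similar gaps under either rule, and they come from small, non-randomised series with different definitions of success. In the B.3 trial the heavier conditional loss came after the first dose (8 of 12) rather than before it (9 of 21), so the first dose is not the point beyond which TAU participants are safe.

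Delivery is also captured elsewhere. D.2.7 plans an induction check-list and records every administered dose, and Table E-6 lists the check-list under Implementation. The primary outcome, BUP at day 7, falls after the induction schedules in Table E-2. This limits the harm but does not repair the named primary implementation measure.

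Finally, the D.3.3 and Table E-6 windows are worded differently, so the two one-dose measures overlap heavily without being strictly identical.

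**Conclusion.** The point holds as one of definition and interpretation. D.3.3 calls initiation completion, leaves induction day undefined, and so cannot answer the question that D.3.2 poses. It conflicts with the use of completion in D.2.7 and B.3 and largely duplicates the one-dose row of Table E-6. The 57% and 19% from B.3 show only that initiation and completion can be far apart. They do not predict this trial's rates.

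Because the first dose comes at a different stage in each arm, the two percentages should not be read as comparable completion rates. No stronger statement about arm advantage is supported. No formal error rate is involved, and the primary outcome and its sample size are unaffected.

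The count of 11 doses rests on the four days shown in Table E-2 and would change if the reconciled schedule differs.

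**What to change.** - Rename the one-dose measure *induction initiation*, keep it as the Table E-6 row, and state which day or window counts as induction day in each arm. It can also serve as the denominator for the D.3.3 linkage benchmark, which already refers to participants who initiate BUP.
- Define *complete induction* as receipt of the last scheduled BUP step of the assigned protocol, and make this the primary implementation measure. First reconcile the descriptions: microdosing is four days in the Specific Aims and in part of D.2.7, but five in B.9, D.2.1 and the D.2.7 rationale. Standard induction is two days in the Specific Aims, while its Table E-2 column runs to Day 4. Which schedule applies is for the investigators to settle.
- Leave agonist cessation out of the common definition. It is the first step in TAU and the last in microdosing, so it is not the same milestone in both arms.
- Score completion from the medication administration record. Show post-discharge doses separately by data source, with participants of unknown status as their own category, and list the EMA dose report as a source in D.3.3, which now names only program logs and EHR data.
- Report both measures by arm as descriptive, and make the construct labels in D.3.3 and Table E-6 agree.

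The cost is wording plus one added data source that is already being collected. The completion percentage will be lower than the one-dose figure. Completion after early discharge will rest partly on self-report, mainly in the microdosing arm, which is why the data source should be shown.
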